## **(2)Statistical analysis**

- 1) the distribution of cases of six groups: the total loss rate of six groups and the loss rate due to adverse events.
- 2) comparability analysis: comparison of demographic data and other baseline values to measure the comparability of the six groups.
- 3) Compliance analysis: compared with the six groups of patients whether they meet the appropriate treatment on time and take the drug banned in the

---

programme.

4)Effectiveness analysis: main efficacy indexes are analyzed by PP (per protocol)and ITT(Intend to treat); Since this study is a multicenter clinical trial, the effect of the central effect and baseline on the efficacy index should be considered.

5)Effect factor analysis: such as age, sex, course of disease, and combination of drugs, etc.

6) Safety analysis: first, according to the requirements of adverse reaction correlation list ,describes six groups of adverse events and adverse reactions, (including the number of cases of adverse events and laboratory test indexes before and after the test , abnormal turn cases and different rate). The adverse reactions were analyzed by chi-square test.

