## **The Study Protocol of the project**

### **Different kinds of acupuncture treatments for Knee Osteoarthritis: a Multi-center Randomized controlled trial**

#### **Research objectives**

(1)The study aims to exam different kinds of acupuncture treatment for treating knee osteoarthritis (KOA), compared with the effective drug control group respectively, and confirm the efficacy of different acupuncture treatments of KOA, and further a safe, effective and easily-spread therapy for KOA.

(2)To observe and compare the effects between groups of different acupuncture treatment: acupuncture group, moxibustion group and warm-needling group, and make clear whether the moxibustion play a key role in the acupuncture treatment for KOA.

(3) To compare the effects of acupuncture group and sham-needle group and make clear whether acupuncture is effective in KOA treatment.

(4) To compare the effects of electro-acupuncture group and the warm-needling group, to explore whether there are different clinical effects of electric stimulation and warm stimulation in acupuncture treatment of KOA.

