## 3. Design and implementation of blind method

The blind(patient-blind) design is adopted in this program, and the patients are evaluated by blind method. Index evaluation and data recording, treatment operator and statistician are all separated. The random member and the therapist know the grouping; The curative evaluators and the statisticians were not aware of the grouping.

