### (3)Statistical analysis method

1) Measurement data: first, the normal test is carried out, and t-test, paired t test, variance analysis, covariance analysis and other methods are adopted if it's in a normal distribution. Rank and inspection, matching rank and check are used for data that does not conform to normal distribution.

2) Counting data: using the chi-square test, Fisher exact test, etc.; The hierarchical data were analyzed by Ridit analysis, CMH(Cochran-mantel-Haensel statistics) or other non-parametric tests.

3) Multicenter analysis of comprehensive curative effect: using CMH method for counting data while analysis of covariance for measurement data.

4) All statistical tests were by bilateral inspection, and the P value was less than or equal to 0.05, which is statistically significant.

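### The only named safety comparison is a chi-square test of adverse reactions; at 60 per arm a non-significant result is weak evidence that a treatment is safe

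*Combined protocol and SAP*

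**What the plan says.** Research objectives, item (1), includes the aim of finding "further a safe, effective and easily-spread therapy for KOA". No safety hypothesis or margin accompanies it.

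Under 6. Statistical processing, (2) Statistical analysis, item 6, the plan "describes six groups of adverse events and adverse reactions". The listed output covers adverse-event counts and laboratory values at both ends of the trial. It then adds "The adverse reactions were analyzed by chi-square test", without saying whether the test is across all six groups or pairwise. Item 1 of the same section also reports "the total loss rate of six groups and the loss rate due to adverse events".

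The general rule for count data in (3) Statistical analysis method is wider: "using the chi-square test, Fisher exact test, etc". The one rule for interpreting any test is that "the P value was less than or equal to 0.05, which is statistically significant", two-sided.

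On blinding, section 3 describes a patient-blind design in which efficacy evaluators and statisticians do not know the group, while "The random member and the therapist know the grouping". Section 5, item (3), lists needle and moxa events to be recorded after each treatment. It lists none specific to the drug arm.

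**The concern.** There are two weaknesses.

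First, a difference test answers a different question from the objective. It can show that rates differ. It cannot show that a treatment is safe, or that two treatments are alike, unless the study is large enough for a null result to exclude differences that matter. This trial was sized on WOMAC function alone.

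Second, the test covers adverse reactions, so an event counts only if someone judges it related to treatment. The plan does not name that person or state whether they are blinded. Therapists do know the arm.

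At stake is the safety half of objective 1. A reader given only a P value could not tell how large an excess of harm the data leave open.

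**Working it through.** **Inputs.** From the plan: 60 patients per group, six groups, two-sided 0.05. The documents state no event rate and no safety sample size, so there is no safety figure to reproduce. The only size calculation is for WOMAC function: 42 per group, then 42/0.8 = 52.5, rounded up to 53, then set at 60. Only the 60 is used here. All event rates below are assumptions.

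**Step 1: the six-group test.** X² = Σ(xᵢ − n·p̄)² / [n·p̄(1 − p̄)], with n = 60, xᵢ the count in arm i and p̄ the pooled rate, compared with the 95th percentile of chi-square on 5 degrees of freedom. Simulated with 40,000 trials per scenario:

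| Five arms | One arm | Power |
|---|---|---|
| 5% | 10% | 17% |
| 5% | 15% | 51% |
| 5% | 20% | 81% |
| 2% | 10% | 57% |

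A doubling from 5% to 10% in one arm would therefore be missed about 83% of the time (100 − 17).

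**Step 2: pairwise tests.** Exact enumeration over both binomial distributions, 60 v 60:

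| Rates | Chi-square | Fisher exact |
|---|---|---|
| 5% v 10% | 17% | 9% |
| 5% v 15% | 46% | 33% |
| 2% v 10% | 46% | 28% |
| 5% v 20% | 73% | 63% |

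By the usual normal approximation, 80% power for 5% v 10% needs 435 per group.

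**Step 3: what a non-significant result leaves open.** Take 6/60 v 3/60. The pooled rate is 9/120 = 0.075. X² = 0.05² / [0.075 × 0.925 × (2/60)] = 0.0025/0.0023125 = 1.08, so P = 0.30. The Newcombe 95% interval for the same 5-point difference runs from −5.2 to +15.7 points.

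**Step 4: an arm with no events.** Solving (1 − p)⁶⁰ = 0.025 gives p = 1 − 0.025^(1/60) = 0.0596, an exact two-sided 95% upper limit of 6.0%. With 48 patients (60 × 0.8, the planned dropout rate) it is 7.4%.

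**Step 5: sparse counts.** Expected events per arm are 60 × 0.05 = 3 and 60 × 0.02 = 1.2, below the customary 5 for chi-square. In simulation with equal rates in all six arms, however, the six-group test rejected 4.6% of the time at both 5% and 2%. The main problem is low information, not a false-positive rate above 5%.

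**The case against.** The strongest reply is that the plan does more for safety than run one test, and that part of it stands. All adverse events are described by group whatever their attribution, along with laboratory indexes and losses due to adverse events, and Fisher's exact test is available for count data. It would be wrong to say that the safety assessment rests on a single chi-square test. None of these provisions, however, supplies an interval or a stated contrast, and Fisher's test has lower pairwise power than chi-square in every scenario above.

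Low power for uncommon harms is also common to trials sized for efficacy, and the power figures rest on assumed rates. For a large excess, one arm at 20% against 5%, the six-group test reaches 81%. This is fair, and it is a reason to report intervals rather than to enlarge the trial.

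Three stronger readings are tempting, and the documents do not support them:

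- **That the trial is open.** Section 3 calls it patient-blind, with blinded efficacy evaluators and statisticians. Masking a capsule against needles or moxa is doubtful, but that is inference.
- **That therapists decide relatedness knowing the arm.** No passage says so, and section 3 separates treatment from evaluation and recording. What can be said is that the assessor and their blinding are not stated. For events such as needle pain or burns there is probably little discretion over attribution.
- **That P above 0.05 will be declared proof of safety.** The plan states no such rule. It is a risk created by having a safety objective and a significance threshold with no estimate planned between them.

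**Conclusion.** The point holds in a limited form. The only safety comparison the plan names is a difference test on a subset of events defined by an unassigned relatedness judgement, and no interval, margin or power supports a conclusion about safety. At 60 per arm a non-significant result is weak evidence: about 17% power when one arm has double an assumed 5% rate, and an upper limit of 6.0% even with no events observed. The upper limit depends only on 60 patients being assessed in the arm; the power figures depend on the assumed rates. Whether attribution would in fact be biased cannot be judged from the documents. The consequence is confined to what the trial can say about safety, so this is a low-severity point with a cheap remedy.

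**What to change.** Replace the chi-square sentence in item 6 with text to this effect:

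- For each arm, report the number and percentage of patients with any adverse event regardless of attribution, and with each listed reaction, with exact 95% confidence intervals.
- For any adverse event, report risk differences with 95% confidence intervals for acupuncture v sham and for each acupuncture or moxibustion arm v Celebrex.
- For procedure-specific events such as needle pain or burns, report rates per arm only. A difference from a capsule arm is nearly built in by the design.
- Where counts are sparse, use exact tests. Treat all safety P values as descriptive, and do not infer safety or absence of difference from P > 0.05.
- State who judges relatedness and whether that person is blinded.

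The contrasts with Celebrex also need a line on how adverse events are collected in that arm. Section 5 requires recording after each acupuncture or moxibustion treatment and sets no matching schedule for the capsule, so a difference could partly reflect how often patients were asked.

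The cost is SAP wording and one extra table. The summaries by arm use counts that item 6 already calls for. The downside for the sponsor is a more cautious safety statement.

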### (3)Statistical analysis method

1) Measurement data: first, the normal test is carried out, and t-test, paired t test, variance analysis, covariance analysis and other methods are adopted if it's in a normal distribution. Rank and inspection, matching rank and check are used for data that does not conform to normal distribution.

2) Counting data: using the chi-square test, Fisher exact test, etc.; The hierarchical data were analyzed by Ridit analysis, CMH(Cochran-mantel-Haensel statistics) or other non-parametric tests.

3) Multicenter analysis of comprehensive curative effect: using CMH method for counting data while analysis of covariance for measurement data.

4) All statistical tests were by bilateral inspection, and the P value was less than or equal to 0.05, which is statistically significant.

### (4) Statistical software

SAS9.3 software analysis.

## **Trial flow chart**
